### 3.1. STUDY OUTCOME MEASURES

Data of interest	Study outcome measures
System / usability data	Data availability: what percentage of essential and optional data fields are available 24/7. System availability: delay in generating response 24/7. Number and nature of technical issues (drop-outs, freezes).
Anonymised patients' data	Patient demographics (age in years, gender, primary diagnosis) Outcomes: organ function (hourly SOFA), ICU and hospital mortality
Bedside physicians' data	Doses administered to patients of intravenous fluids and vasopressors, which are action chosen by on-duty clinicians
Evaluators' data (the doctors assessing the AI in the background)	Evaluator's grade and seniority A custom-made interface linked to a database will capture and record the following: 
 
- What dose they would recommend, before and after seeing the AI suggested dose.
 
- Agreement with AI suggested dose: does it appear appropriate, too high or too low?
 

## 4. PARTICIPANT ENTRY

### 4.1. INCLUSION CRITERIA

#### For patients:

Adult patient > 18 years old

Admitted to an intensive care unit

Likely or confirmed diagnosis of sepsis as per sepsis-3 definition (as defined in the glossary)

ICU length of stay > 24h

#### For evaluators:

ICU doctors at the senior registrar, ICU fellow or consultant level

## 4.2. EXCLUSION CRITERIA

### For patients:

Not for full active care, e.g. not for vasopressors

Not expected to survive more than 24h

Elective surgical admission (these patients are regularly on antibiotics but given as a prophylaxis, with no sepsis)

Opted-out for use of their data for research (NHS and NHS-X website)

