### Hypotheses:

- We are able to run the system with high availability, reliability and acceptable lag (near real-time) at the bedside.
- The quality of AI suggestions, assessed by off-duty clinicians, is appropriate.
- Patients' outcomes are better when actual doctors' decisions match the suggested AI decisions (which remain hidden from on duty doctors).

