## 3. STUDY DESIGN

This study is a prospective multi-centre observational study that will include four intensive care units from two different NHS Trusts.

The duration of the study will be up to 24 months.

We will include 100 to 300 adult patients with early sepsis in ICU (within 24h of ICU admission). This number is a pragmatic, realistic estimate of how many patients will satisfy the inclusion criteria in the study period (assuming a conservative 60 admissions per month on each unit (reality is closer to 80-100 pre-COVID-19), and 20% sepsis at admission), and will allow us to deliver on the study objectives.

With regards to human assessors, we will include 6 to 15 ICU doctors, mixing senior registrars, ICU fellows and consultants.

The “system” will be a purpose built webapp accessed from a dedicated laptop, connected to an NHS ICT server, with secure login. It will be linked to a duplicate of the Philips ICCA database (Imperial College Healthcare NHS Trust) or the EPIC EHR (UCLH) which contains ICU patient data in near real time (estimated lag of 5 to 15

minutes). The system will be running the AI Clinician algorithm, which processes ICU patient data and outputs a suggested dose of intravenous fluids and vasopressors. Four times a day (every 6 hours), the system analyses newly admitted ICU patients and identify those who fulfil the sepsis-3 criteria. If they do, they will be added to a list of patients for potential inclusion that will be accessible from within the software (and assessed by human evaluator for enrolment).

The system will contain several tabs:

- 1- **Patient screening.** It displays a list of patients screened and highlighted by the system as fulfilling sepsis-3 criteria. The user (human evaluator) has the option to include them into the study, after verification of the inclusion/exclusion criteria (see sections 4.2 and 4.3 for these criteria).
- 2- **Individual patient data.** This screen contains a drop-down list of patients included in the study. After selecting one, the data time series of this individual patient are displayed here, along with the doses of fluids and vasopressors actually given by human “on-duty” doctors and nurses.

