Routine clinical data (demographics, diagnosis, severity of illness, presence and duration of mechanical ventilation, ICU and hospital length of stay and hospital mortality, see appendix for more specific information) will be collected until hospital discharge from the recruiting centre. All outcome data will be collected from hospital databases including microbiology results.

To determine how the tool was implemented at each site, a trained researcher will accompany all site initiation visits to make observations and take field notes regarding discussions of planning and implementation at site.

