## 4.3. WITHDRAWAL CRITERIA

### For evaluators:

Requested withdrawal from study. Human evaluators may request withdrawal by contacting the study coordinators. In the event that an evaluators request withdrawal from the study, no further data will be collected from them.

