## 7. STATISTICS AND DATA ANALYSIS

Data and all appropriate documentation will be stored for a minimum of 10 years after the completion of the study, including the follow-up period.

Data of interest	Statistical analyses
-------------------------	-----------------------------

System / usability data	Simple descriptive statistics (e.g. average system lag, number of technical issues per week...)
Anonymised patients' data	Simple descriptive statistics of the patient characteristics. Comparison of the training and prospective cohorts (simple parametric and non-parametric tests comparing demographics, severity of illness, etc).
Evaluators' data (the doctors assessing the AI in the background)	Descriptive statistics from evaluators data: Agreement between initial human evaluator doses (data point #1) and AI decisions (data point #2), and between AI decisions (data point #2) and actual doses given to patients (data point #3). Proportion of AI decisions (data point #2) classified as appropriate / possibly too low / possibly too high Proportion of human decisions (data point #3) classified as appropriate / possibly too low / possibly too high
AI decisions evaluation	Quantitative analyses of AI decisions: estimate patients' outcomes if the AI decisions were followed and compare them to actual outcomes (which were linked with human decisions). We will use 2 methods: 1) compare short-term outcomes between model-concordant treatment and model-non-concordant treatment, with confounder adjustment; 2) off-policy policy evaluation of the AI policy in the prospective ICHT cohort.

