## Appendix 2. Summary of required data fields.

Category	Items	Format	Unit	Comment
Cohort selection	Patient unique identifier	Integer/code	-	
Cohort selection	Date and time of administration of antibiotics	Date	-	Any oral or IV antibiotic (no topical, e.g. cream or eye drops)
Cohort selection	Date and time any blood or urine culture sent for MCS	Date	-	

Demographics	Age	Continuous	days or years	
Demographics	Gender	Binary	-	
Demographics	Weight at the time of ICU admission	Continuous	kg	
Demographics	Readmission to intensive care	Binary	-	Has this patient already been admitted to ICU during this hospital stay ?
Demographics	Comorbidities/past medical history (ICD codes)	Free text	-	if possible!
Demographics	Delay between hospital admission and ICU admission	Date	hours	
Demographics	ICU and hospital mortality	Binary	-	
Vital signs	Glasgow coma scale	Continuous	-	
Vital signs	Heart rate	Continuous	bpm	
Vital signs	Systolic blood pressure	Continuous	mmHg	
Vital signs	Mean blood pressure	Continuous	mmHg	
Vital signs	Diastolic blood pressure	Continuous	mmHg	
Vital signs	Respiratory rate	Continuous	bpm	
Vital signs	SpO2 = pulse oxymetry	Continuous	%	
Vital signs	Temperature	Continuous	Celsius	
Lab values	Potassium	Continuous	meq/L	
Lab values	Sodium	Continuous	meq/L	
Lab values	Chloride	Continuous	meq/L	
Lab values	Glucose	Continuous	mg/dL	
Lab values	BUN = Blood Urea Nitrogen = Urea	Continuous	mg/dL	
Lab values	Creatinine	Continuous	mg/dL	
Lab values	Magnesium	Continuous	mg/dL	
Lab values	Calcium	Continuous	mg/dL	
Lab values	Ionised Calcium	Continuous	mg/dL	
Lab values	CO2 : total CO2	Continuous	meq/L	
Lab values	SGOT	Continuous	u/L	
Lab values	SGPT	Continuous	u/L	
Lab values	Total_bilirubin	Continuous	mg/dL	
Lab values	Albumin	Continuous	g/dL	
Lab values	Hb = Haemoglobin	Continuous	g/dL	
Lab values	WBC count	Continuous	E9/L	

Lab values	Platelets count	Continuous	E9/L	
Lab values	PTT = Partial Thromboplastin Time	Continuous	s	
Lab values	PT = prothrombin time	Continuous	s	
Lab values	INR = International Standardized Ratio	Continuous	-	
Blood gas	Arterial_pH	Continuous	-	
Blood gas	paO2	Continuous	mmHg	
Blood gas	paCO2	Continuous	mmHg	
Blood gas	Arterial base excess	Continuous	meq/L	
Blood gas	Arterial lactate	Continuous	mmol/L	
Blood gas	HCO3 = bicarbonate	Continuous	meq/L	
Ventilation parameters	Mechanical Ventilation	Binary	-	Is the patient mechanically ventilated?

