Ventilation parameters	Interface for oxygen administration	categorical	-	E.g. face mask, nasal cannulae...
Ventilation parameters	Flow of oxygen	Continuous	L/min	Helps estimating the effective FiO2
Ventilation parameters	FiO 2 = inspired fraction of oxygen	Continuous	-	May not be documented if there is a flow of O2 in L/min
Medications and fluid balance	Intravenous Fluid intake	Continuous	mL	IV crystalloids given for resuscitation
Medications and fluid balance	Vasopressor	Continuous	mcg/kg/min	Includes infusions of noradrenaline, adrenaline, phenylephrine, vasopressin, metaraminol, dopamine
Other interventions	Renal replacement therapy	Categorical	-	any indication that the patient is undergoing acute dialysis for acute renal failure
Other interventions	Sedation	Continuous	-	any continuous infusion of propofol, midazolam, fentanyl, remifentanyl, thiopental, atracurium, rocuronium

Medications and fluid balance	Urine output	Continuous	mL	Includes items such as -- "Foley" -- "Void" -- "Condom Cath" -- "Ileoconduit" -- "Suprapubic" -- "Nephrostomy" -- "Ureteral Stent"
Medications and fluid balance	Cumulated fluid balance since ICU admission	Continuous	mL	
Preadmission data	Total IV fluid intake prior to ICU admission	Continuous	mL	
Preadmission data	Total urine output prior to ICU admission	Continuous	mL

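### Limitation of treatment is screened for only at entry and no listed field records it later, so it is an unmeasured confounder of the AI-concordance comparison and the off-policy evaluation

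*Protocol*

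**What the plan says.** Protocol section 4.2 lists, among the patient exclusions, "Not for full active care, e.g. not for vasopressors". Section 3 says when the criteria are applied: the evaluator includes a patient from the screened list "after verification of the inclusion/exclusion criteria". Section 4.3, on withdrawal, deals with evaluators only ("Human evaluators may request withdrawal by contacting the study coordinators").

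Routine clinical data "will be collected until hospital discharge from the recruiting centre" (section 3). Appendix 2, titled "Summary of required data fields", covers cohort selection, demographics, vital signs, laboratory values, blood gases, ventilation, fluids and drugs, renal replacement, sedation and pre-admission data. Mortality is a binary item there, and section 8.3 says that the date of death is not needed.

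Section 7 plans two outcome analyses of the AI decisions. The first is to "compare short-term outcomes between model-concordant treatment and model-non-concordant treatment, with confounder adjustment"; the second is an off-policy evaluation in the ICHT cohort. They serve the last secondary objective and the third hypothesis in section 1.2, that "outcomes are better when actual doctors' decisions match the suggested AI decisions".

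**The concern.** The entry exclusion implies that doses given under a treatment limitation say little about how sepsis should be dosed. The protocol follows that reasoning at inclusion and has no provision for it afterwards. A patient who enters on full care and later has care limited stays in the data, and the doses recorded from then on follow from the limitation.

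Such a limitation is related both to the dose given, and so to whether it matches the AI, and to death. That makes it a confounder. No listed field records it, so the adjustment in method 1 cannot include it. Method 2 draws on the same records and lacks the same variable. What is at stake is the reading of hypothesis 3: an association between matching decisions and survival could partly reflect that clinicians had already limited care in patients who then died.

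**Working it through.** **Check of the text.** I looked for a later application of the exclusion, a patient withdrawal rule, or a field for a limitation.

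- Sections 3 and 4.2: one check, at inclusion.
- Section 4.3: evaluators only.
- Section 3.1 (outcome measures) and Appendix 2: no item for limitation, withdrawal of support or palliative care, and no time for any of these.
- Section 3 adds ICU and hospital length of stay. This may approximate the time of an in-hospital death, but not the time of a limitation.

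**Illustration of size.** The protocol gives no figure for this bias, so there is none to reproduce. Suppose that concordance has no true effect.

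Inputs:
- m = mortality. 30% is assumed. The only figure in the protocol is 48,000/250,000 = 19.2% (section 1.1, all UK sepsis, not an ICU rate).
- c = share of decisions that are concordant without a limitation, 40% (assumed).
- s = share of deaths preceded by a limitation, 25% to 75% (assumed); L = m × s. All limited patients are taken to die.
- Five decision periods per patient, the last of them after the limitation where there is one (assumed).
- q = concordance in that last period, 0 at first (assumed).

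Per patient enrolled:
- Concordant decisions: C = 5(1 − L)c + 4Lc + Lq
- Those belonging to patients who die: D = 5(m − L)c + 4Lc + Lq
- Mortality with concordant decisions = D/C; with non-concordant decisions = (5m − D)/(5 − C)

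For s = 50%: L = 0.15, C = 1.70 + 0.24 = 1.94 and D = 0.30 + 0.24 = 0.54. This gives 0.54/1.94 = 27.8% against 0.96/3.06 = 31.4%.

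| m | s | Concordant | Non-concordant | Gap (points) |
|---|---|---|---|---|
| 30% | 25% | 0.57/1.97 = 28.9% | 0.93/3.03 = 30.7% | 1.8 |
| 30% | 50% | 0.54/1.94 = 27.8% | 0.96/3.06 = 31.4% | 3.5 |
| 30% | 75% | 0.51/1.91 = 26.7% | 0.99/3.09 = 32.0% | 5.3 |
| 19.2% | 25% | 0.3648/1.9808 = 18.4% | 0.5952/3.0192 = 19.7% | 1.3 |
| 19.2% | 50% | 0.3456/1.9616 = 17.6% | 0.6144/3.0384 = 20.2% | 2.6 |
| 19.2% | 75% | 0.3264/1.9424 = 16.8% | 0.6336/3.0576 = 20.7% | 3.9 |

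For scale, the 10% relative mortality reduction claimed in section 1.1 is 0.10 × 30% = 3.0 points, or 0.10 × 19.2% = 1.9 points.

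**Direction.** Keep m = 30% and s = 50%, and vary concordance after the limitation:
- q = 20%: 0.57/1.97 = 28.9% against 0.93/3.03 = 30.7%, a gap of 1.8 points in favour of concordance.
- q = 40% (equal to c): 0.60/2.00 = 30.0% against 0.90/3.00 = 30.0%, no gap.
- q = 60%: 0.63/2.03 = 31.0% against 0.87/2.97 = 29.3%, a gap of 1.7 points against concordance.

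The sign therefore depends on whether concordance falls after a limitation. With no decisions counted after the limitation, the gap in this model is zero.

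No calculation was made for the off-policy evaluation. The point there rests on the missing variable alone.

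**The case against.** The strongest reply is that much of this belongs to a SAP, which is not shown: the definition of concordance, the outcome window, the confounders and any censoring rule. That is fair for the analysis rule. It does not dispose of the field, because a SAP cannot adjust for or censor on something the study has not undertaken to collect.

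A second reply is that Appendix 2 is not exhaustive. Length of stay and microbiology results appear in section 3 without a row there, and the identity lookup stays within the trusts, so a limitation time could be retrieved. That stands. It would be wrong to say that the gap cannot be repaired; the protocol simply does not commit to closing it.

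Third, the listed physiology, ventilation, sedation and renal replacement data could capture part of the decline before a limitation, and exclusion of patients not expected to survive 24 hours narrows the problem at entry. Both would reduce the bias, and the figures above are unadjusted. Neither removes it, since the decision to limit care is not itself recorded.

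A reader might also infer two stronger things.

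- *That the bias must favour the AI.* The model aims at survival and no limitation input is listed, so continued active suggestions are likely. The protocol does not show them, however, and a limitation may be a ceiling under which current doses continue.
- *That the gap could be near 19 points.* Classing each patient by the last decisions gives, at m = 30%, c = 40% and s = 50%, 0.06/0.34 = 17.6% against 0.24/0.66 = 36.4%. The protocol proposes no such classification, and it is the least favourable one for this bias.

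**Conclusion.** The concern holds as one of unmeasured confounding. The exclusion operates at entry only, a later limitation is not among the listed data, and both outcome methods in section 7 would be exposed to it if run as written.

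The direction is probable, not established: towards hypothesis 3 if concordance falls after a limitation, absent if it is unchanged, and the reverse if it rises. The size is unknown. About 2 to 5 points at 30% mortality is an illustration resting on assumed mortality, concordance, share of deaths with a limitation, five periods and complete discordance afterwards, with no adjustment. It shows only that the bias could be comparable with the claimed 3-point effect. It refers to mortality; method 1 uses short-term outcomes, and for SOFA the direction is less certain.

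The reach is limited to the last secondary objective, hypothesis 3 and, to a lesser degree, the AI-versus-actual agreement. The primary objective, technical reliability, is untouched. The change should be made, but the study does not stand or fall on it.

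**What to change.** - **Appendix 2:** add one field, the date and time of the first documented limitation of active treatment, taken from the trust record.
- **Section 7:** leave decisions after that time out of method 1, method 2 and the agreement between AI and actual doses. Keep the patient and the outcome in the analysis. Report how many patients and decisions are affected, and show results with and without those decisions.

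The cost is one more item to extract from two record systems (ICCA and EPIC). The entry check cannot supply it, because the event comes later. Fewer decisions remain for analysis. Censoring at limitation may itself be informative, since a limitation can follow deterioration under earlier doses; that is why both versions should be reported. Clinical care does not change.

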### For both patients and evaluators:

Declined participation

No patient consent is required

## 4.3. WITHDRAWAL CRITERIA

### For evaluators:

Requested withdrawal from study. Human evaluators may request withdrawal by contacting the study coordinators. In the event that an evaluators request withdrawal from the study, no further data will be collected from them.

## 5. ADVERSE EVENTS

It is an observational study, so there is no direct risk for patients or the human evaluators. Adverse events involve data security questions, in particular data breach and loss of personal identifiable information. These aspects are addressed in section 8.3 “confidentiality”.

## 6. ASSESSMENT AND FOLLOW-UP

There will be no follow-up. The study ends at each participating site, at the time of hospital discharge of the last recruited patient.

## 7. STATISTICS AND DATA ANALYSIS

Data and all appropriate documentation will be stored for a minimum of 10 years after the completion of the study, including the follow-up period.

Data of interest	Statistical analyses
-------------------------	-----------------------------

System / usability data	Simple descriptive statistics (e.g. average system lag, number of technical issues per week...)
Anonymised patients' data	Simple descriptive statistics of the patient characteristics. Comparison of the training and prospective cohorts (simple parametric and non-parametric tests comparing demographics, severity of illness, etc).
Evaluators' data (the doctors assessing the AI in the background)	Descriptive statistics from evaluators data: Agreement between initial human evaluator doses (data point #1) and AI decisions (data point #2), and between AI decisions (data point #2) and actual doses given to patients (data point #3). Proportion of AI decisions (data point #2) classified as appropriate / possibly too low / possibly too high Proportion of human decisions (data point #3) classified as appropriate / possibly too low / possibly too high
AI decisions evaluation	Quantitative analyses of AI decisions: estimate patients' outcomes if the AI decisions were followed and compare them to actual outcomes (which were linked with human decisions). We will use 2 methods: 1) compare short-term outcomes between model-concordant treatment and model-non-concordant treatment, with confounder adjustment; 2) off-policy policy evaluation of the AI policy in the prospective ICHT cohort.

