## 1. INTRODUCTION

### 1.1. BACKGROUND

Sepsis is life-threatening organ dysfunction due to severe infection and affects 250,000 patients annually in the UK (pre-COVID-19), of whom 48,000 die. In addition, virtually all COVID-19 intensive care unit (ICU) deaths had sepsis. It is a leading cause of death and the most expensive condition treated in hospitals. It was recognised as a top research priority by the James Lind Alliance, a partnership of patients and clinicians to prioritise the most pressing unanswered questions facing the NHS.

The cornerstone of sepsis resuscitation is the administration of intravenous fluids and/or vasopressors (drugs that squeeze the blood vessels to increase blood pressure) to maintain blood flow to prevent organ failure. However, there is huge uncertainty around the individual dosing of these drugs in an individual patient, partially due to high sepsis heterogeneity. The current guidelines provide recommendations at a population-level but fail to individualise the decisions. Wrong decisions lead to poorer outcomes and increased ICU-resource use. A tool to personalise these medications could improve patient survival.

We have developed a new method to automatically and continuously review and recommend the correct dose of these medications to doctors, which was created using artificial intelligence (AI) techniques applied to large medical databases. The method we used is called reinforcement learning. In this framework, we model patients with sepsis in the ICU as belonging to a large number of possible disease states, and we analyse what interventions are likely to help them transition to healthier states, and

eventually to survival. We demonstrated in our initial publication that the value of the AI selected strategy was on average reliably higher than human clinicians. In a large validation cohort independent from the training data, mortality was lowest in patients where clinicians' actual doses matched the AI decisions: mortality rates rose, in a dose dependent manner, as the clinicians' actual decisions diverged from the AI decisions. We have estimated that our AI algorithm could reduce mortality by 10% (in relative terms), which represents over 1,000 lives saved annually in the UK and would scale to hundreds of thousands of lives worldwide. Now, we intend to start clinical testing of this AI technology in the UK.

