- 3- **Evaluation tab.** This is where the evaluation of the AI and human doctors’ decisions takes place. The option to scroll through the various previous time points is provided. The evaluation by the human evaluator takes place in several subsequent steps: First, the human evaluator makes a recommendation based on patient data alone (data point #1). Then, the human evaluator is presented with the AI recommendation (data point #2), along with other information (confidence in the suggested decision, explanation of why this action was recommended). They “rate” the AI decisions, by classifying the AI suggested actions in different categories, such as “likely safe”, “likely inappropriate”, “possible too low”, or “possibly too high”. Finally, the human evaluator is presented with the actual decision (made by human clinicians, data point #3) and the subsequent patient evolution (at least a few hours, but the final outcome of ICU death or survival will be presented if available). The human evaluators rate the actual decisions using the same scale, e.g. “likely safe”, “likely inappropriate”, etc. There will be a free-text box to enable the user to provide feedback on their decisions.

The software will be accessed on the dedicated laptop from within the NHS hospitals by off-duty clinicians enrolled in the study, whom we call “human evaluators”. To explore system’s usability around the clock, there will be no restrictions with regards to timing of the research, so the human evaluators will be able to conduct the research at any time and on any day of the week.

We intend to conduct the study during 1-hour sessions, during which the users will conduct these 2 actions:

- 1) Identify new patients for inclusion from a pre-screened list
- 2) Assess multiple decisions made on multiple included patients. Based on a conservative number of 5 patients with sepsis on each unit at any point in time, and between 4 - 10 sessions per user, we will gather a maximum of 600 to 1,500 data points (100 data points per user for 6 to 15 users). We expect to include an estimated

100 to 300 separate patients across 4 sites (based on 20 patients per month per unit and 27 months of total study period over the 4 units, which gives 540 potential eligible patients). This will enable to complete the study objectives.

Data about the system's operational reliability will be automatically collected:

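### Section 7 names only significance tests for comparing the training and prospective cohorts; these mix size of difference with an open sample of 100 to 300 and cannot show that the cohorts are alike

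*Protocol*

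**What the plan says.** The table in Protocol Section 7 has a row for anonymised patient data with two entries. The first is "Simple descriptive statistics of the patient characteristics". The second is the comparison of the training and prospective cohorts, for which the method given is "simple parametric and non-parametric tests comparing demographics, severity of illness, etc". The protocol names no standardised difference, confidence interval, margin or significance level for this comparison, and no rule for interpreting its result.

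Section 3 gives a prospective sample of 100 to 300 patients and explains it this way: "This number is a pragmatic, realistic estimate of how many patients will satisfy the inclusion criteria in the study period". The supporting count is a recruitment projection, "based on 20 patients per month per unit and 27 months of total study period over the 4 units, which gives 540 potential eligible patients". The training data are described only in general terms; Section 1.1 says of the method: "which was created using artificial intelligence (AI) techniques applied to large medical databases".

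**The concern.** Comparing the two cohorts is useful because the algorithm was learned on one set of patients and is now run on another. What a reader needs is the size of the difference in age, severity and so on, and how precisely it is known. A significance test answers a different question, namely whether the data are compatible with no difference at all, and its answer changes with the number of patients.

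Here that number may vary threefold, so the same difference can come out as significant or not according to recruitment. With about 100 patients, a table of non-significant tests could look reassuring when it only reflects a small sample. With about 300, a small difference may be flagged without any indication of whether it is large enough to matter. The comparison is background to the evaluators' ratings of the AI decisions and to the "off-policy policy evaluation of the AI policy in the prospective ICHT cohort", so readers are likely to consult it when judging those results.

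**Working it through.** **The plan's own figure.** 20 patients per unit per month × 27 unit-months = 540 potentially eligible patients, which matches Section 3. This is a recruitment count. No power or precision figure is stated for the cohort comparison, so there is none to reproduce.

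**Inputs**
- Prospective sample n: 100 to 300 (Section 3).
- Training sample N: not stated. Assumed 10,000, with 1,000 and 100,000 as the range.
- Two-sided 5% level: assumed, since none is stated.
- Differences are in SD units, for a continuous variable with a common SD.

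**Formulas**
- Standard error of the standardised difference: SE = √(1/n + 1/N). The further term that depends on the difference itself is negligible here.
- Smallest observed difference reaching p<0.05: 1.96 × SE. This is also the half-width of the 95% interval.
- Power for a true difference d: approximately Φ(d/SE − 1.96).

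**Standard errors at N = 10,000**
- n = 100: √(0.01 + 0.0001) = 0.1005, and 1.96 × 0.1005 = 0.197 SD.
- n = 300: √(0.00333 + 0.0001) = 0.0586, and 1.96 × 0.0586 = 0.115 SD.

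**Power for a true difference of 0.2 SD at N = 10,000**
- n = 100: 0.2/0.1005 − 1.96 = 0.03, so power is 51%.
- n = 300: 0.2/0.0586 − 1.96 = 1.45, so power is 93%.

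**Sensitivity to the assumed training size**

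| Training N | Smallest significant difference, n=100 | n=300 | Power at 0.2 SD, n=100 | n=300 |
|---|---|---|---|---|
| 1,000 | 0.206 SD | 0.129 SD | 48% | 86% |
| 10,000 | 0.197 SD | 0.115 SD | 51% | 93% |
| 100,000 | 0.196 SD | 0.113 SD | 52% | 93% |

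The prospective sample dominates the standard error, so the unknown training size changes little.

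**One observed difference, three sample sizes.** For an observed 0.15 SD with N = 10,000, p = 0.136 at n = 100, 0.036 at n = 200 and 0.011 at n = 300. As an interval, the same result is 0.15 ± 0.197 = −0.05 to 0.35 SD at n = 100, and 0.15 ± 0.115 = 0.035 to 0.265 SD at n = 300. At n = 100 the test is non-significant, yet the interval still allows a difference of about a third of an SD.

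**Where the size of difference decides the result.** At n = 100 and N = 10,000, power is 17% at 0.1 SD, 51% at 0.2 SD, 85% at 0.3 SD and 99.9% at 0.5 SD. At 0.5 SD it is at least 99.8% for every n from 100 to 300 and every N in the table. For observed differences, dependence on enrolment is confined to roughly 0.12 to 0.20 SD, the band between the two significance limits.

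**The case against.** The strongest reply is that this is a one-line sketch of a secondary, descriptive comparison, that the descriptive statistics in the same table row may show the size of any difference, and that effect measures and intervals belong in a statistical analysis plan. Part of this stands. The comparison is not tied to the primary objective, and a separate analysis plan may well add effect sizes. But the protocol does not leave the method open: it names tests and nothing else. The descriptive entry does not say that it covers the training cohort, and it carries no interval.

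A reader might infer more than the document supports:
- *That the result depends on enrolment alone.* It depends on both enrolment and the size of difference; a 0.5 SD difference would be found at any planned sample size.
- *That the plan treats p>0.05 as showing comparable cohorts.* No such rule appears, and similarity of cohorts is not among the hypotheses in Section 1.2 or the objectives in Section 2. That reading is a risk in use, not a stated intention.
- *That many chance findings will arise because every field in Appendix 2 is tested.* Section 7 mentions demographics, severity of illness and an open remainder. Appendix 2 lists required data fields, including an identifier and outcomes, and is not a list of tests.
- *That the case for carrying the model over to these patients rests on these tests.* The protocol also evaluates the AI directly in the prospective patients, through evaluator ratings, concordant versus non-concordant treatment, and off-policy evaluation. None of these is conditional on the cohort comparison.

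**Conclusion.** The point holds as a minor one. The stated method is poorly matched to the question of how different the cohorts are, because it merges the size of difference with a sample that may be anywhere from 100 to 300 and has no precision basis. With a training cohort of about 10,000, the significance limit moves from about 0.20 SD to 0.115 SD across the planned range, and a true difference of 0.2 SD goes undetected about half the time at the lower end. A non-significant result cannot support a claim that the cohorts are alike.

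The figures rest on an assumed training size, a two-sided 5% level and a continuous variable with a common SD. The conclusion is stable for training sizes from 1,000 to 100,000. The primary objective, operational reliability, is unaffected.

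**What to change.** In the patient-data row of the Section 7 table, replace the tests with, or at least accompany them by, the standardised difference between the training and prospective cohorts and its 95% interval for each baseline variable compared. Add that any statement about similarity will rest on these estimates and intervals, not on p-values.

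The expected half-width is about 0.20 SD with 100 patients and 0.11 to 0.13 SD with 300. The estimate then does not shift systematically with enrolment; only its precision does. Little is lost by the change, since an interval that excludes zero corresponds closely to a significant test.

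The cost is one line of text and no new data. The downside is small: with close to 100 patients the intervals will be wide, and the statement on similarity may be less favourable than a column of non-significant p-values would suggest. A check on how many prospective patients fall in disease states that are rare in the training data would be a separate analysis with its own definitions and cost, and is not part of this change.
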